2.3 Study Population

Subjects eligible to participate in this study must meet all of the following inclusion criteria:

- Males that are 18 years or older with established severe haemophilia A as evidenced by their medical history. Subjects will be considered as severe if their base FVIII level is 1 IU/dL or less
- Treated/exposed to FVIII concentrates or cryoprecipitate for a minimum of 150 exposure days (EDs)
- Greater or equal to 12 bleeding episodes only if on on-demand therapy over the previous 12 months. Does not apply to subjects on prophylaxis
- Able to sign informed consent and comply with requirements of the trial
- No history of inhibitor, and results from a modified Nijmegen Bethesda assay of less than 0.6
 Bethesda Units (BU) on 2 consecutive occasions at least one week apart within the past 12
 months
- Sexually active subjects must be willing to use an acceptable method of contraception such as
 double barrier, including hormonal contraception for at least 6 months post treatment. After 6
 months, subjects may stop contraception use only if they have had 3 consecutive negative semen
 samples.

Subjects are not eligible for this study if they meet any of the following exclusion criteria:

- Detectable pre-existing immunity to the AAV5 capsid as measured by AAV5 transduction inhibition or AAV5 total antibodies
- Any evidence of active infection or any immunosuppressive disorder.
- HIV positive

Proprietary and Confidential Pg. 10 of 38

- Significant liver dysfunction as defined by abnormal elevation of:
 - o ALT (alanine transaminase) to 3 times the upper limit of normal;
 - o Bilirubin above 3 times the upper limit of normal;
 - o Alkaline phosphatase above 3 times the upper limit of normal; or
 - o INR (international normalized ratio) ≥ 1.4
- Potential participants who have had a liver biopsy in the past 3 years are excluded if they had significant fibrosis of 3 or 4 as rated on a scale of 0-4
- Evidence of any bleeding disorder not related to Haemophilia A
- Platelet count of $< 100 \times 10^9/L$
- Creatinine $\geq 1.5 \text{ mg/dL}$
- Liver cirrhosis of any etiology as assessed by liver ultrasound
- Hepatitis B if surface antigen is positive
- Hepatitis C if RNA is positive
- Treatment with any IP within 30 days prior to the end of the screening period
- Any disease or condition at the physician's discretion that would prevent the patient from fully

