3.5 Handling of Dropouts and Missing Data

If a subject withdraws from the study prior to the Week 260 visit, the subject will be asked to complete an Early Termination Visit (ETV).

Missing dates or partially missing dates will be imputed conservatively for concomitant medications and adverse events (AEs) to ensure that an AE is considered treatment emergent and the duration is the longest possible duration.

FVIII activity levels below the LLOQ (Lower limit of quantitation) will be imputed with 0 IU/dL.

Missing data will not be imputed unless otherwise stated. The main analyses will be observed cases (no imputation), in some cases supported by repeated measures approaches.

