11.1 Primary Efficacy Endpoint(s)

Plasma FVIII activity will be determined by validated assays, one-stage clotting and chromogenic substrate assays, assessed by the central lab. Plasma FVIII activity will be assessed weekly for 36 weeks after BMN 270 infusion and continue to have the regularly scheduled assessments as planned in the protocol. The true steady-state of plasma FVIII activity level produced from BMN 270 can only be assessed after a minimum of 72 hours has elapsed since the last infusion of FVIII protein concentrates. Therefore, FVIII activity levels within 72-hours after FVIII use will be excluded from analysis. FVIII activity levels below the LLOQ (Lower limit of quantitation) will be imputed with 0 IU/dL. If FVIII activity level is retested, the retest assessment will be used for all analyses. A listing of original test assessment and retest assessment will be provided.

The primary efficacy endpoints will be:

- Responder/nonresponder status, where a responder is defined as a subject with median FVIII activity of ≥ 5 IU/dL during week 13-16 post-BMN 270 infusion
- Median FVIII activity during week 13-16

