The above ABR analyses will be repeated for treated bleeds, as defined using standard criteria defined by the Subcommittee on Standards and Criteria, FVIII/FIX subcommittee of the International Society of Thrombosis and Hemostasis. A bleed is considered to be a "treated bleed" if it is directly followed by a haemophilia medication reported to be a "treatment for bleeding episode" irrespective of the time between the treatment and the preceding bleed (i.e., there is not an intervening bleed). A bleed and the first treatment thereafter are considered to be pairs (i.e., one treatment belongs to one bleed only), with the following exception: if multiple bleeds occur on the same calendar day, the subsequent treatment is considered to apply for each of these multiple bleeds (which are, however, counted as separate treated bleeds). Bleeds due to surgery/procedure are not included in the primary analysis. Only treatments that were recorded as "treatment for bleeding episode" are included in the determination of a treated bleed. Two bleeds at the same anatomical location are considered to be one bleed if the second occurs within 72 hours from the last treatment for the first bleed. The last treatment is defined as the last treatment before a new bleed occurs, either in the same or in a different location. This is in line with the above definition that bleeds and treatments are considered to be pairs.

The Annualized FVIII use and Annualized FVIII infusion rate will be analyzed similarly as ABR. The post-infusion and pre-infusion annualized FVIII use will be compared using a paired t-test. The FVIII replacement treatment by the following different categories will also be summarized:

- Treatment for adverse events (including all bleeds, and symptoms associated with the development of a bleed or bruises that would occur in a non-haemophiliac person per protocol)
- Treatment for bleeding episode (including all bleeds, and symptoms associated with the
 development of a bleed or bruises that are normal events of haemophilia but should not be
 treated as AEs per protocol)
- Prophylaxis (routine)
- Surgery/procedure
- Prophylaxis (precautionary due to activity/injury)

The analyses described for the secondary endpoints will be conducted for the FAS analysis population. Sensitivity analyses using PP analysis population may be performed for secondary endpoints, if applicable.

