11.2.1 Correlation between FVIII Activity and Bleeding Risk

FVIII activity is widely acknowledged to be a key aspect of hemophilia A and a valuable indicator of patients' status, while annualized bleeding rate has been traditionally used as the primary clinical endpoint for replacement therapy. The correlation between FVIII activity level and bleeding risk has been researched, showing that increases in FVIII activity levels are predictably associated with a decreased number of annual bleeds (Den Uijl, 2011, Haemophilia). The following analyses will be performed to explore the relationship between measured FVIII activity and bleeding in this study.

- Based on the FVIII activity visit windows (Appendix 1), median FVIII activity and total number of treated bleeds (defined in Section 11.2) will be calculated for each window for every subject. A negative binomial regression will be performed, modelling number of bleeds in each window vs. FVIII activity in the window. The analysis will be done for FVIII activity measured by one-stage clotting assay and chromogenic assay separately. The same analyses will be conducted for treated joint bleeds. The analysis will use observed cases and be performed for the Full Analysis Set.
- Using a cutoff of FVIII activity level, e.g., 40 IU/dL, each subject's data will be divided into 2 periods: from Week 5 to the first time reaching 40 IU/dL, and from the first time reaching 40 IU/dL to the end of efficacy period. For each period, the duration of the period, the number of bleeds, the ABR, and the change in ABR from baseline will be listed and summarized. The analysis will be performed using various cutoffs, such as 5, 15, 25, 30, 40 IU/dL.

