Week 76	Day 533	Days [519, 546]
Week 80	Day 561	Days [547, 574]
Week 84	Day 589	Days [575, 602]
Week 88	Day 617	Days [603, 630]
Week 92	Day 645	Days [631, 658]
Week 96	Day 673	Days [659, 686]
Week 100	Day 701	Days [687, 714]
Week 104	Day 729	Days [715, 742]
Week 110	Day 771	Days [743, 791]
Week 116	Day 813	Days [792, 833]
Week 122	Day 855	Days [834, 875]
Week 128	Day 897	Days [876, 917]
Week 134	Day 939	Days [918, 959]
Week 140	Day 981	Days [960, 1001]
Week 146	Day 1023	Days [1002, 1043]
Week 152	Day 1065	Days [1044, 1085]
Week 158	Day 1107	Days [1086, 1127]
Week 164	Day 1149	Days [1128, 1169]
Week 170	Day 1191	Days [1170, 1211]
Week 176	Day 1233	Days [1212, 1253]
Week 182	Day 1275	Days [1254, 1295]
Week 188	Day 1317	Days [1296, 1337]
Week 194	Day 1359	Days [1338, 1379]
Week 200	Day 1401	Days [1380, 1421]
Week 206	Day 1443	Days [1422, 1463]
Week 212	Day 1485	Days [1464, 1505]
 Week 218	Day 1527	Days [1506, 1547]

Proprietary and Confidential Pg. 36 of 38

Week 224	Day 1569	Days [1548, 1589]
Week 230	Day 1611	Days [1590, 1631]
Week 236	Day 1653	Days [1632, 1673]
Week 242	Day 1695	Days [1674, 1715]
Week 248	Day 1737	Days [1716, 1757]
Week 254	Day 1779	Days [1758, 1799]
Week 260	Day 1821	Days [1800, 1841]

For early termination visit (ETV), the window of last derived visit before ETV will end at one day before ETV

Proprietary and Confidential Pg. 37 of 38

^a Relative to the infusion day (day 1)

^b Visit day is calculated by (visit date – date of infusion date + 1) if post infusion and (visit date – date of infusion date) if before infusion

^c Baseline visit value is defined as the last available measurement prior to dosing.

^d FVIII activity assay values within 72-hour interval since last FVIII use are excluded prior to windowing derivation.

^e PCR collection to occur until at least 3 consecutive negative results are obtained. Subjects who have not had 3 consecutive negative samples by Week 52 should continue to have PCR testing every 4 weeks (during Year 2) or every 6 weeks (during Years 3-5) until 3 consecutive negative samples are documented (or upon consultation between the Investigator and Medical Monitor).

^f Urine test starts with week 4, 8, 12, 16, the corresponding windows are Days [2, 42], Days [43, 70], Days [71, 98], Days [99, 126], respectively.

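### In the Section 11.2.1 regression, FVIII given for a bleed can remove its own window from the model, so the fitted bleeding rate is modestly too low

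*SAP*

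**What the plan says.** The first analysis in SAP Section 11.2.1 is a negative binomial regression, "modelling number of bleeds in each window vs. FVIII activity in the window". It is run for each assay and again for treated joint bleeds. The rule for missing values is "The analysis will use observed cases and be performed for the Full Analysis Set".

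Four other rules bear on it:

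- Section 11.1: "Therefore, FVIII activity levels within 72-hours after FVIII use will be excluded from analysis".
- Appendix 17.1, footnote d, fixes the order of the steps: "FVIII activity assay values within 72-hour interval since last FVIII use are excluded prior to windowing derivation".
- Section 3.5: "Missing data will not be imputed unless otherwise stated". Nothing is stated otherwise for this regression.
- Section 11.2, on treated bleeds: "A bleed and the first treatment thereafter are considered to be pairs".

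On sampling, Section 11.1 says "Plasma FVIII activity will be assessed weekly for 36 weeks after BMN 270 infusion". For FVIII activity, Appendix 17.1 then lists one target day per window from Week 56 to Week 260.

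**The concern.** The outcome is a count of bleeds that were treated, ordinarily with FVIII. The predictor is discarded when it was measured within 72 hours of FVIII use. If a window has only one FVIII sample and FVIII for a bleed was given shortly before it, the window has no predictor. The observed-case rule then removes the row together with every bleed in it. A window with no FVIII use keeps its value and stays in as a zero.

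So the chance that a row is missing depends on its own outcome. Deleting such rows lowers the bleeding rate fitted to the rows that remain. At stake is the level of the curve relating bleeding to measured FVIII. The largest absolute loss is at low FVIII, where most bleeds occur.

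**Working it through.** The SAP states no expected rate or dispersion for this regression, so there is no planned figure to reproduce.

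**1. Windows with one scheduled value (Appendix 17.1).** There are 14 post-baseline FVIII windows up to Week 52, including the overlapping Week 23-26. There are 13 for Weeks 56-104 and 26 for Weeks 110-260. The single-day windows number 13 + 26 = 39, out of 14 + 39 = 53 (52 without the overlapping one).

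**2. Is the sample inside the reach of a bleed in the same window?** The Week 60 target is Day 421 in Days 407-434, which is 14 days after the window opens. The Week 116 target is Day 813 in Days 792-833, which is 21 days after. The 72 hours before the sample therefore lie in the same window.

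**3. Chance that one treated bleed empties its window.** Let q = c/L, with c the days blocked and L the window length. One infusion blocks c = 3 days. Three daily infusions (assumed) block c = 5.

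| | L = 28 | L = 42 |
|---|---|---|
| c = 3 | 3/28 = 10.7% | 3/42 = 7.1% |
| c = 5 | 5/28 = 17.9% | 5/42 = 11.9% |

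**4. Expected count in a window that survives.** Let μ be the true mean count and a the negative binomial dispersion, with each bleed deleting the window independently with probability q.

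- Poisson: E[bleeds | kept] = μ(1 − q).
- Negative binomial: E[bleeds | kept] = μ(1 − q)/(1 + a·q·μ).

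Assume 12 bleeds per year at FVIII 0. The SAP gives no post-infusion rate; 12 is borrowed from its entry criterion for on-demand subjects ("Greater or equal to 12 bleeding episodes only if on on-demand therapy over the previous 12 months"). With c = 3, q·μ = 12 × 3/365.25 = 0.0986 for either window length. Kept rate divided by true rate:

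| | L = 28 | L = 42 |
|---|---|---|
| Poisson, any rate | 0.893 | 0.929 |
| a = 1, 12/yr | 0.893/1.0986 = 0.813 | 0.929/1.0986 = 0.845 |
| a = 1, 2/yr (q·μ = 0.0164) | 0.893/1.0164 = 0.878 | 0.929/1.0164 = 0.914 |

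Under Poisson the proportional loss is the same at every bleeding rate, so the log-linear slope is untouched. Only when a > 0 does the proportional loss grow with the rate and flatten the slope.

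**5. Simulation over all Appendix windows.** Week 23-26 was left out. Assumptions: 12 bleeds per year at FVIII 0, log-rate slope −0.08 per IU/dL, a log window-length offset, and two-weekly FVIII in Weeks 37-52 (taken from the inhibitor and antigen windows).

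| Dispersion, days blocked | Rate at FVIII 0: all → kept windows | Ratio | Slope: all → kept | Ratio, Week 56 on only |
|---|---|---|---|---|
| 0, 3 | 12.02 → 11.23 | 0.934 | −0.0799 → −0.0797 | 0.918 |
| 0, 5 | 12.05 → 10.72 | 0.890 | −0.0805 → −0.0804 | 0.875 |
| 1, 3 | 11.74 → 10.32 | 0.879 | −0.0789 → −0.0771 | 0.854 |
| 1, 5 | 11.86 → 9.84 | 0.830 | −0.0798 → −0.0775 | 0.767 |

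No zero-bleed window was lost in any scenario. At FVIII below 5 IU/dL, 10-18% of windows with a bleed were lost.

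Further runs read the rate at 1 IU/dL and took dispersion up to 2. The fitted rate was 7-12% too low under Poisson and about 13-28% too low with dispersion 1-2. The slope moved 0-2% and 3-16% respectively. Interpolating FVIII from adjacent evaluable windows restored both level and slope.

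**The case against.** A reader might infer that the plan flattens the FVIII-bleeding relation, and that naming a negative binomial model shows overdispersion will be present. The SAP supports neither. The negative binomial has the Poisson as its limit, Section 11.2 tests for overdispersion before using it for ABR, and no dispersion value is given anywhere. Under Poisson counts the slope, which is the main interest of an analysis meant to explore a relationship, does not move. Nor is the loss confined to low FVIII: under Poisson it is proportionally equal at every level and only its absolute size is largest there.

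The size also has to be seen against a trial of up to 15 subjects. In simulations of 15 subjects with dispersion 1, the slope moved by 0.001-0.002 against a sampling SD of 0.024-0.032, and the log rate at 1 IU/dL moved by 0.11-0.20 against an SD of about 0.34-0.35. Under Poisson, however, the log rate moved by 0.07-0.11 against an SD of 0.05, so the level bias is not lost in the noise in every case.

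Three further limits stand:

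- Appendix 17.1 lists target days, not a cap on samples. Unscheduled samples, or visits moved after FVIII use under the protocol (not at hand), would reduce the loss.
- Subjects with very low FVIII may resume prophylaxis, so 12 bleeds per year sustained to Week 260 may be too high.
- A reader might extend the problem to the bleeding endpoints. The ABR analyses count all bleeds in each period, and the second analysis in Section 11.2.1 splits time at first reaching a threshold. Neither needs a FVIII value in every window.

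These points limit the size and reach of the bias. They do not remove the selection: the SAP foresees contaminated samples, yet gives no fallback value and no count of lost windows.

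**Conclusion.** The point holds as a modest downward bias in the fitted bleeding rate of one exploratory regression. It follows from the SAP's own rules taken together and arises by schedule in the 39 windows from Week 56 on. Under 12 bleeds per year at FVIII 0 and 3 to 5 blocked days per bleed, the fitted rate is about 7-12% too low with Poisson counts and about 13-28% too low with dispersion 1-2. All of these inputs are assumptions, and the higher range depends on overdispersion that the SAP does not quantify. A flattened slope is conditional on that same overdispersion and should not be stated as a consequence of the plan. This is a change to consider, not one on which the trial's conclusions depend.

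**What to change.** In Section 11.2.1, keep the 72-hour exclusion. For any window in this regression that the exclusion leaves without a FVIII value, assign FVIII by linear interpolation between that subject's adjacent evaluable windows, or from the nearest evaluable window if only one side exists. The window and its bleeds then stay in the model. Keep the observed-case fit as a sensitivity analysis and report how many windows and bleeds it drops.

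The cost is about two sentences in the SAP and a little programming. The small downside is the assumption that endogenous FVIII changes slowly between adjacent windows.

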11.3 Other Efficacy Endpoint(s)

The Haemo-QoL-A is a patient-reported outcome (PRO) questionnaire which will be used to assess subject quality of life (QoL) during the study. Change from Baseline will be summarized for the total score and subscale scores (physical functioning, role functioning, worry, consequences of bleeding, emotional impact, treatment concern). Graphic summary of mean QoL change over time will be provided

Proprietary and Confidential Pg. 19 of 38

for the total score and each subscale scores. Mixed model for repeated measures (MMRM) may be performed to analyze the change from baseline in PROs. The 95% CIs of the mean changes may be provided.

FVIII activity by both one-stage clotting and chromogenic substrate assays will also be assessed at local labs at the same time points as when they will be by the central lab. A data listing of local FVIII activity assessments will be provided. The analyses for central FVIII activity assessments will be conducted, if needed.

The analyses described in this section will be conducted for the FAS.

11.4 Examination of Efficacy by Subgroups

The following subgroup analyses may be examined for key efficacy endpoints by dose cohort:

- Baseline FVIII treatment regimen: On-demand vs. prophylactic therapy
- Baseline Age: 18-29 years vs. 30-50 years vs. >50 years old
- Race
- History of target joint(s)

These analyses will be conducted for the FAS analysis population.

12.0 SAFETY EVALUATIONS

Safety will be assessed by adverse event reporting; clinical laboratory assessments, with particular attention to liver tests; vital signs assessments; physical examinations; and immunogenicity. Safety analyses will be carried out for the Safety analysis population. No formal statistical testing will be performed; only summary statistics will be provided, unless otherwise noted.

12.1 Adverse Events

Only treatment-emergent adverse events (TEAEs) occurring and reported during the study period will be included in the adverse event summaries. A TEAE is defined as any AE that newly appeared, increased in frequency, or worsened in severity following initiation of study drug administration. Adverse events will be coded in accordance with Medical Dictionary for Regulatory Activities (MedDRA).

An adverse drug reaction (ADR) is any AE for which there is a reasonable possibility that the study drug caused the AE. The investigator will assess the causality for individual AEs, applying the guidance specified in protocol, and those assessed as study drug-related will be considered ADRs.

A serious adverse event (SAE) is any untoward medical occurrence that at any dose meets one or more of the seriousness criteria enumerated in the protocol. AE severity, not equivalent to seriousness, will be assessed using the protocol defined categories using the NCI CTCAE v4.03.

All bleeding events and suspected bleeding events, regardless of the need for exogenous FVIII therapy as treatment, should be captured in subject diaries and recorded on the designated bleeding eCRF. Bleeding

Proprietary and Confidential Pg. 20 of 38

events and suspected bleeding events should not be reported as adverse events, with the following exception:

 All bleeding events and suspected bleeding events which meet one or more of the criteria for being serious (refer to protocol Section 10.2) should be reported as serious adverse events (whether or not they are bleeding events that are normal sequelae of haemophilia, and whether or not they required exogenous FVIII as treatment).

The study AE reporting period is as follows: After informed consent but prior to initiation of study treatment, only SAEs associated with any protocol-imposed interventions will be reported. After informed consent is obtained and the administration of study drug, the reporting period for all non-serious AEs and SAEs begins and continues for approximately 5 years or until study discontinuation/termination, whichever is later.

The following types of AEs will be summarized: all AEs, AEs assessed by investigator as related, SAEs, SAEs assessed by investigator as related, AEs leading to study discontinuation, deaths, EOSIs. Listings will be provided.

If the onset date or end date of an AE is partial, the same imputation rules described in Section 3.5will be applied.

12.1.1 All Adverse Events

The incidence and number of events for all TEAEs will be summarized by system organ class (SOC), preferred term (PT) and severity for each dose cohort and overall. For those AEs that occurred more than once during the study, the maximum severity will be used to summarize the AEs by severity. In addition to TEAE listing, a listing of AEs reported under Investigations SOC will also be provided.

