2.2 Study Design

This is a first-in-man, phase 1/2 open-label, dose escalation study in subjects with severe haemophilia A. Eligible subjects will enter the dose escalation part of the study, followed by a 16-week Post-Infusion Follow-Up period during which safety and efficacy assessments will be taken. After the primary endpoint analysis at 16 weeks, safety and efficacy will then be assessed for approximately 5 years.

Subjects who provide written informed consent, meet the entry criteria definition of severe HA, and do not have transduction inhibition activity to AAV5 will be eligible to enroll in the study. Participants will be enrolled into one of up to four cohorts according to dose level as a single intravenous (IV) infusion:

Cohort 1: 6E12 vector genomes [vg] per kilogram of body weight

Cohort 2: 2E13 vg per kilogram

Cohort 3: 6E13 vg per kilogram Cohort 4: 4E13 vg per kilogram

The starting dose was based on the expression and safety of FVIII observed in nonclinical studies of mice and monkeys. The starting dose has a significant safety margin (10-fold) from no observed adverse effect level (NOAEL) in mice.

Cohort 1-3

The first 3 cohorts will be enrolled sequentially, allowing a period of 3 weeks or more between cohorts. Dose escalation may occur after a single subject in a cohort has been safely dosed if the resulting FVIII activity at the Week 3 visit is < 5 IU/dL in both the one-stage clotting and chromogenic substrate assays. If the FVIII activity reaches ≥ 5 IU/dL at the Week 3 visit and no safety issue is found, then the remaining subjects in the cohort will be enrolled without the need to wait for 3 weeks between subjects. The flow chart of dose escalation scheme for Cohorts 1 to 3 is shown in Figure 2.2.1. Three weeks is expected to be the time the expression will be close to the maximum. This escalation paradigm is intended to minimize the subject numbers exposed to subtherapeutic doses. The decision to escalate to the next dose level will be made based on the review of safety parameters and FVIII activity by the Sponsor and a panel of investigators participating in the study.

Patient 1: 6E12 Optimum number of patients per dose: ≥ 5% <5% Patient 2-4: 6E12 Patient 2: 2E13 2E13 N=1-4 N=4+ ≥ 5% <5% Patient 5-8: 2E13 Patient 3-5: 2E13 Patient 3: 6E13 <5% ≥ 5% Stop

Figure 2.2.1: Flow Chart of Dose Escalation Scheme for Cohorts 1 to 3

Cohort 4

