For Cohort 4, 3 subjects will be enrolled at 4E13 vg/kg. If FVIII activity in these 3 subjects is \geq 5% at 8 weeks and if no safety issue is found, an additional 3 subjects may be enrolled in this cohort.

All Cohorts

There will be an ongoing review of individual subject safety and efficacy data by the medical monitor and

Proprietary and Confidential Pg. 9 of 38

the DRB. The adaptive nature of this trial allows the DRB to recommend allocating subjects to the cohorts based on activity levels of FVIII and safety signals.

Because subjects develop neutralizing immunity upon exposure to the AAV5 capsid, re-challenge of vector is not a likely treatment option, and these subjects have effectively a single opportunity for therapy using this AAV capsid. Efficacy will be determined by FVIII activity at 16 weeks post-dose. Safety will be evaluated for approximately 5 years after dosing. Any safety signal may trigger a review of the data and possible additional immunogenicity studies that include an assessment of cellular immune responses using collected peripheral blood mononuclear cells (PBMC). Additionally, if any of the events listed in protocol Section 9.3.4.1 occur, enrollment into the trial will be halted to complete an extensive safety analysis. Notification of the study enrollment halt will be sent by the Sponsor to the participating sites via telephone and email immediately after becoming aware of a safety concern. This will ensure no additional subjects are dosed until the signal has been completely evaluated. If, following safety review by the DRB and the Sponsor, it is deemed appropriate to restart dosing, a request to restart dosing with pertinent data will be submitted to the health authority.

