2.6.3 Interim Analysis

No formal interim analysis is planned. An analysis of the primary endpoint will be done following all subjects having completed the study assessments through the end of the Post-Infusion Follow-Up Period (Week 16).

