5.0 DISCONTINUATION AND COMPLETION

For treated subjects who prematurely discontinue study participation prior to the Week 26 visit, prior to the Week 52 visit and overall, the primary reason for discontinuation will be summarized by dose cohort.

Proprietary and Confidential Pg. 13 of 38

The number and percentage of subjects who are continuing the study, who completed Week 104, and who completed Week 156 will also be provided for all treated subjects overall and by dose cohort.

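### Adverse event tables by dose cohort have no common time window, so at a data cut before all subjects reach Week 260 a longer-followed cohort can look more toxic from observation time alone

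*SAP*

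**What the plan says.** **Tables.** Section 12.1.1, where the columns are the cohorts and a total: "The incidence and number of events for all TEAEs will be summarized by system organ class (SOC), preferred term (PT) and severity for each dose". Sections 12.1.2 and 12.1.3 use the same by-cohort layout for drug-related events, serious events and serious drug-related events.

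**Period covered.** Section 12.1: "Only treatment-emergent adverse events (TEAEs) occurring and reported during the study period will be included in the adverse event summaries". For treated subjects, AE reporting "continues for approximately 5 years or until study discontinuation/termination, whichever is later". Section 2.2 gives the planned length for all cohorts: "Safety will be evaluated for approximately 5 years after dosing".

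**Entry of cohorts.** Section 2.2: "The first 3 cohorts will be enrolled sequentially, allowing a period of 3 weeks or more between cohorts". Cohort 4 starts with three subjects. If the 8-week FVIII activity and safety conditions are met, "an additional 3 subjects may be enrolled in this cohort". The lag from Cohort 3 to Cohort 4 is not given.

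**Reporting before the end.** Section 5.0 tabulates, by cohort, subjects "who are continuing the study, who completed Week 104, and who completed Week 156".

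**Use of the tables.** Section 3.0 says safety will be looked at in relation to dose level. Section 12.0 rules out formal testing unless otherwise noted. Section 10.0 summarises follow-up time but does not connect it to any adverse event measure.

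**The concern.** Safety is the first primary objective, and the by-cohort tables are where a reader will look for a relation between dose and toxicity. Both measures in them, the proportion of subjects with an event and the number of events, rise with time under observation. If cohorts have been followed for different lengths of time when a table is produced, part of any difference between columns is calendar time and not dose.

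The SAP does adjust for time elsewhere. Section 11.2 divides bleeds, FVIII use and FVIII infusions by days observed, and Appendix 17.1 sets windows for FVIII activity, laboratory tests, quality of life, shedding and antibodies. The general adverse event tables have neither a rate nor a window.

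The direction matters too. If the lower doses were given first, extra follow-up raises their event figures and can mask a rise with dose. If 4E13 was dosed after 6E13, as the cohort numbering suggests but the SAP does not state, extra follow-up would widen the contrast between those two doses.

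**Working it through.** The SAP gives no adverse event rate or power figure, so there is none to reproduce. The check asks how far the tables differ when the true risk is identical in two cohorts.

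**Inputs from the SAP**
- Minimum gap between successive cohorts among Cohorts 1 to 3: 3 weeks. Cohort 1 to Cohort 3 is therefore at least 3 + 3 = 6 weeks (Section 2.2).
- Milestones: Week 16 (Section 2.6.3), Weeks 104 and 156 (Section 5.0), Week 260 (Section 3.5 and Appendix 17.1).

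**Assumptions**
- The same constant event rate in both cohorts, at 0.3 or 1 event per person-year.
- A 52-week lag and a Week 156 against Week 104 split, both for illustration only.

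**Formulas**, with T in weeks and 52.18 weeks per year
- Event-count ratio per subject = T(earlier) / T(later)
- Incidence = 1 − exp(−rate × T / 52.18)

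| Situation | T earlier / later | Count ratio | Incidence at 0.3 per year | Incidence at 1 per year |
|---|---|---|---|---|
| 6-week lag, later cohort at Week 16 | 22 / 16 | 1.38 | 12% v 9% | 34% v 26% |
| 6-week lag, later cohort at Week 104 | 110 / 104 | 1.06 | 47% v 45% | 88% v 86% |
| Assumed 52-week lag, later cohort at Week 16 | 68 / 16 | 4.25 | 32% v 9% | 73% v 26% |
| Assumed Week 156 v Week 104 | 156 / 104 | 1.50 | 59% v 45% | 95% v 86% |
| All at Week 260, fixed window | 260 / 260 | 1.00 | 78% v 78% | 99% v 99% |
| AE reporting to study termination, 6-week lag | 266 / 260 | 1.02 | 78% v 78% | 99% v 99% |

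The last row takes the later-of-the-two wording in Section 12.1 literally: earlier-dosed subjects would stay under AE reporting until the last subject finishes. At the stated minimum lag this hardly matters.

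**Check on the remedy.** A window completed by both cohorts makes the two T values equal, so the ratio is 1.00 at any cut. This does not require a constant rate. Events per subject-year give 1.00 only if the rate is constant. Suppose instead that each subject has one event soon after infusion and none later. The whole-study rate is then 1/3 = 0.33 per year after 3 years and 1/2 = 0.50 after 2 years, so the longer-followed cohort looks safer although the risk is the same.

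**The case against.** The case against is substantial, and most of it stands.

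- **Planned follow-up is equal.** Each subject is to be followed for about 5 years. A reader might infer that earlier-dosed cohorts will look more toxic in the final report. The SAP does not support that: with completers and a fixed window the ratio is 1.00. The distortion needs an earlier cut or unequal withdrawal.
- **The only stated lag is short.** A reader might take the Week 104 and Week 156 rows in Section 5.0 to mean that one cohort will be a year ahead of another. Section 5.0 only counts subjects reaching each milestone and assigns no cohort to either. A large distortion between 6E13 and 4E13 is equally undocumented, because that lag is not given.
- **The Week 16 analysis concerns the primary efficacy endpoint.** Section 2.6.3 says: "An analysis of the primary endpoint will be done following all subjects having completed the study assessments through the end of the Post-Infusion Follow-Up Period". It does not schedule adverse event tables, so the Week 16 row shows what would happen if they were run then.
- **Several early toxicities are already tied to time.** Section 12.1.5 gives time to onset for events of special interest, unless otherwise specified, and a 48-hour window for infusion reactions. Section 12.2 plots ALT at 4-week intervals by cohort. These do not cover the general, drug-related and serious event tables.
- **Numbers are very small.** At most 15 subjects are dosed (Section 2.5), and a cohort may hold only one. In a cohort of six, one subject is 17 percentage points, so the 14-point gap in the Week 156 v Week 104 row is less than one subject. Chance will dominate. That limits the importance of the point but is no reason to leave in a systematic difference that costs almost nothing to remove.

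**Conclusion.** The point holds as a conditional one. The by-cohort tables for all, drug-related and serious adverse events run over all available follow-up without a common window. Because Section 5.0 foresees reporting with subjects still continuing, a longer-followed cohort can look more toxic from observation time alone at any cut before all subjects reach Week 260, or where withdrawal differs between cohorts.

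At the minimum lag the SAP states, the effect is moderate early (about 1.38 in event counts with the later cohort at Week 16) and slight later (about 1.06 at Week 104). The ratios of 1.5 and 4.25 rest on assumed lags. All the figures assume equal, constant event rates. The comparison is descriptive and the cohorts are tiny, so this is an inexpensive improvement in reporting. It does not invalidate the safety analysis, and no dose or clinical rule is involved.

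**What to change.** In Sections 12.1.1 to 12.1.3, for any analysis run before all subjects have completed Week 260:

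1. Add by-cohort tables of all, drug-related and serious adverse events restricted to a post-infusion window that every cohort has completed, for example infusion to Week 16 or to Week 52. Show how many subjects in each cohort completed the window, since withdrawal inside it is not corrected by the restriction.
2. Print person-years by cohort beside the whole-study table, using the follow-up time already summarised under Section 10.0.
3. If events per subject-year are shown, give them within period only. A whole-study rate dilutes early post-infusion events over long follow-up and biases the comparison the other way.
4. State in Section 12.1 whether the final tables close at a fixed point of about 5 years for each subject or run to study termination, so that it agrees with Section 2.2.

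The cost is SAP wording, a period flag and repeat runs of existing tables. No new data are needed. The drawback is a few more tables with small counts and many empty cells, so one or two windows are enough.
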